The pulse oximeter, the Heartbeat application (MediBeat), and the supervisor's smartphone (Samsung Galaxy Xcover 4 with Bluetooth connectivity) will be charged, and tested each day of interactions with participants. Prior to conducting the study session, the equipment will have to be calibrated for each participant. The first step of the calibration process is to manually enter the reference data (date of birth, height, weight, baseline manual blood pressure reading and heart rate). Once data is entered, and participant has been given 10 minutes of rest, the nurse supervisor will ensure the participant is seated comfortably, with their legs uncrossed, back supported, and their arm rested on the table at heart level. The nurse supervisor will then attach the Contec finger pulse oximeter to the participant's finger (opposite to the arm with the manual blood pressure cuff) and wait for a few seconds, to make sure a stable signal is received, and the device displays both the participant's pulse and SpO₂ values. Once the values are displayed, the nurse supervisor will hit the "Add session" button, and choose the correct device to connect to via Bluetooth. The calibration process will begin, indicated by the orange background, and the MediBeat application will display the participant's heartrate and SpO₂ values. It is critical that the participant does not move during the calibration process, which will last just over 1 minute. The background of the application will turn blue once calibration has completed successfully.

Recruitment plan

Inclusion/Exclusion Criteria

Healthy participants who are over the age of 25 and live or work in the North Simcoe Muskoka and Markham regions will be recruited to participate in this study. As outlined in the ESH-IP, only healthy subjects will be included this study; those who have heart arrhythmias, atrial fibrillations or atrial flutters, an inaudible Korotkoff sound, wounds of the upper arms/wrists, missing fingers, and/or an arm circumference of more than 55 cm will be excluded, in advance if at all possible, and at the study site if not previously excluded.

Recruitment will continue until the following quotas are met:

1. Numbers: At least 85 who fully complete the study protocol, and fall within the parameters listed in #3
2. Sex: At least 26 male and 26 female (each 30% of the total number of participants)

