Boxes 346–348: The observer measurements (three per subject) for SBP are categorised similarly to the recruitment ranges. Enter the counts of measurements falling into each range. These must total 99 (Boxes 281, 283 and 285).

Box 349: Subtract the smallest value from Boxes 346 to 348 from the largest one and enter the result.

Box 350: Enter the lowest pressure, a colon and the highest DBP from the observer measurements (Boxes 282, 284 and 286).

Boxes 351–353: The observer measurements (three per subject) for DBP are categorised similarly to the recruitment ranges. Enter the counts of measurements falling into each range. These must total 99 (Boxes 282, 284 and 286).

Box 354: Subtract the smallest value from Boxes 351 to 353 from the largest one and enter the result.

- In order to ensure a uniform distribution, there must be at least 22 measurements and at most 44 measurements (Boxes 346 to 348 and 351 to 353) in each of the low, medium and high ranges and the maximum differences (Boxes 349 and 354) must be at most 19. If not, further recruitment will be necessary. Subjects to be excluded will be those whose pressures drifted from recruitment pressures.
- The overall SBP range must be from ≤ 100 mmHg to ≥ 170 mmHg and the overall DBP range must be from ≤ 50 mmHg to ≥ 120 mmHg. If not, further recruitment will be necessary. Subjects to be excluded will be the last recruited within the relevant ranges.
- The minimum number of replacements should take place. If a subject is replaced for either of these reasons, circle *Distribution* in *Box 287 of Form 2* for that subject.
- In validations carried out in specific populations requiring more than 33 subjects but with similar blood pressure distributions, similar proportions should be used. If the blood pressure distribution in the specific population differs from the standard distribution, ignore this table but comment on the distribution in the discussion.

Table 4 Observer differences

This section is for the differences in pressures between the two observers

Observer 2–Observer 1	SBP	DBP	Repeated measurements
	Range (Low : High)	355	356
	Mean (SD)	357	358

Boxes 355–356: Enter the lowest difference, a colon and the highest difference between the observers. Include the signs e.g. $-3:+4$. (Boxes 247, 249, 251 and 253 and Boxes 248, 250, 252 and 254). If the range is outside $-4:+4$, then this is a violation. Relevant subjects should be excluded, by reason of Observer Disagreement, and replaced.

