Appendix O – International Protocol Accuracy Criteria

ESH International Protocol 2010			
Sequential Measurements			
IP Grading Part 1 - Minimum Requirements (at least 255 pairs of individual measurements)			
N	≤ 5 mmHg	≤ 10 mmHg	≤ 15 mmHg
Two of	188	224	247
All of	167	209	240
IP Grading Part 2 (85 subject mean pressures)			
N	$2/3 \leq 5$ mmHg		$0/3 \leq 5$ mmHg
At least	62		
At most			8
Recruitment Ranges (n = 85)			
SBP		DBP	
mmHg	Subjects	mmHg	Subjects
90*...129	26 – 31	40*...79	26 – 31
130...160	26 – 31	80...100	26 – 31
161...180*	26 – 31	101...130*	26 – 31
*	Altogether, up to 4 recruitment pressures are permitted to be outside these limits.		
Test Measurement Distribution			
SBP		DBP	
mmHg	Measurements	mmHg	Measurements
≤ 100	≥ 3	≤ 50	≥ 3
< 130	57 – 113*	< 80	57 – 113*
130...160	57 – 113*	80...100	57 – 113*
> 160	57 – 113*	> 100	57 – 113*
≥ 170	≥ 3	≥ 120	≥ 3
*	The difference between the maximum and minimum of these 3 counts for SBP and, separately, for DBP, must be less than or equal to 19.

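### Form 3 Table 3 keeps the 33-subject distribution limits (total 99, 22–44 readings per range), which 85 subjects cannot meet and which contradict the 57–113 in Appendix O

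*Combined protocol and SAP*

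**What the plan says.** **Sample.** The recruitment plan asks for "At least 85 who fully complete the study protocol, and fall within the parameters listed in #3", with 26–31 subjects in each of three systolic and three diastolic ranges. Appendix O puts this at "at least 255 pairs of individual measurements".

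**Form 3 (Appendix N), Table 3 Distribution.** For systolic pressure, "The observer measurements (three per subject) for SBP are categorised similarly to the recruitment ranges"; diastolic is handled in the same way. The instruction continues: "Enter the counts of measurements falling into each range. These must total 99". The first note under the table says that "there must be at least 22 measurements and at most 44 measurements" in each of the low, medium and high ranges, and that "the maximum differences (Boxes 349 and 354) must be at most 19". The consequence follows: "If not, further recruitment will be necessary. Subjects to be excluded will be those whose pressures drifted from recruitment pressures". A second note sets overall pressure ranges as a separate requirement, and a subject replaced for either reason is coded Distribution on Form 2. A last note asks for proportional limits above 33 subjects, but only for validations in specific populations.

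**Appendix O, Test Measurement Distribution.** For 85 subjects, each of the same three ranges must hold 57–113 readings. The largest and smallest counts may differ by at most 19.

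**Which document governs.** The Data Analysis section sends the analysis to Form 3. It cites Appendix O for passing parts 1 and 2 of the accuracy grading. Neither that section nor any other states which appendix prevails on the distribution check.

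**The concern.** The distribution check helps decide who is analysed. When it fails under Table 3, completed subjects can be removed and others recruited, and Form 3 leaves excluded subjects out of all its results. Form 3 also makes a pass conditional on every protocol requirement being met.

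Two appendices give incompatible limits for this one check, and the form named for the analysis carries the limits that 85 subjects cannot meet. A sample that satisfies Appendix O would be non-compliant on Form 3. Anyone acting on Form 3 would have to choose subjects to remove for drift after Form 2 is complete, when each subject's device error is already on the page. In a study meant to support applications to Health Canada and the FDA, that is an avoidable opening for bias and for a dispute over compliance.

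**Working it through.** **Inputs**
- Completers: at least 85 (recruitment plan); at most 3 × 31 = 93 if every range is filled to 31.
- Readings per subject: 3 systolic and 3 diastolic (Form 3, Table 3).
- Form 3 limits: total 99, 22–44 per range, difference at most 19.
- Appendix O limits: 57–113 per range, difference at most 19.

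**1. Reproduce the plan's figures.** Form 3's total is 33 × 3 = 99. At 85 subjects it is 85 × 3 = 255, as in Appendix O. Scaling the range limits by 255/99:
- 22 × 255/99 = 56.7, which rounds to 57.
- 44 × 255/99 = 113.3, which rounds to 113.

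Appendix O's 57–113 is therefore Form 3's 22–44 rescaled to 85 subjects.

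**2. Can 255 readings meet Form 3?**
- Most readings that fit under the cap: 3 × 44 = 132, or 132/3 = 44 subjects.
- Smallest possible count in the fullest range: 255/3 = 85, which exceeds 44.

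Enumerating every split of the readings over three ranges confirms this:

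| Readings | Range limits | Max. difference | Admissible splits |
|---|---|---|---|
| 99 | 22–44 | 19 | 361 |
| 255 | 22–44 | none | 0 |
| 279 (93 subjects) | 22–44 | none | 0 |
| 255 | 57–113 | 19 | 379 |
| 255 | 57–113 | 49 | 2,269 |

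Form 3's limits work at 33 subjects and fail for every split at 85. Appendix O's limits can be met.

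**3. The limit of 19.** Unlike 22 and 44, this was not rescaled: 19 × 255/99 = 48.9, about 49. Its effect at 255 readings follows directly.
- Let the smallest count be m. The other two are at most m + 19, so 3m + 38 ≥ 255 and m ≥ 72.3, that is 73.
- Let the largest count be M. The other two are at least M − 19, so 3M − 38 ≤ 255 and M ≤ 97.7, that is 97.

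Every count must lie in 73–97. While 19 stands, 57–113 never binds.

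**4. A fixed total of 255 would not do either.** At 93 subjects there are 279 readings. The proportional limits are then 22 × 279/99 = 62 and 44 × 279/99 = 124.

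**The case against.** The best defence is that Form 3 is the standard ESH form attached unchanged. The list of appendices marks Appendix M as amended and does not mark Appendix N. The Protocol section says the ESH procedure is modified to at least 85 subjects. Appendix O is written for that number, and Form 3's own notes show that limits are meant to scale above 33. A sensible analyst would use 57–113.

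Much of this stands. It disposes of a stronger reading: that the replacement rule fires in every possible sample, or at every data check. That is true only of Form 3 read alone and at the full sample. Appendix O's limits can be met. The four daily checks under Data Checking contain no 22–44 limit, and during recruitment up to 44 subjects could still fit under the cap. Wrongful removal of subjects would require staff to follow Form 3 against Appendix O. That is a risk, not a certainty.

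The defence does not remove the conflict.
- The Data Analysis section names Form 3 for the analysis and ties Appendix O to the accuracy grading, not to the distribution check.
- Form 2 sends the reader to Form 3 for exclusions due to changes in pressure.
- The scaling note is confined to specific populations. Form 3 contrasts these with a general adult population fixed at 33, and this study recruits healthy adults generally.
- The recruitment plan says its 26–31 per range is shown in Form 3, whereas Form 3 says 10–12. The protocol assumes an updated form that is not the one attached.

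**Conclusion.** The point holds as an internal contradiction. Form 3 Table 3 is wrong as written for this study: its cap admits 132 readings (44 subjects) against at least 255 (85 subjects), and its total of 99 is met only at 33 subjects. Appendix O has the right scaling of the range limits, and nothing says that it prevails. The conclusion rests only on counting, with three readings per included subject and at least 85 included.

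A reader might also infer that correcting 22–44 would reduce the number of replacements. Measured against Appendix O, the documents do not support that: the difference limit of 19 already confines counts to 73–97, so it is what would trigger replacement under either wording of the range limits. The correction removes a contradictory rule; it does not loosen the check that Appendix O sets.

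The sponsor should make the change. It concerns who may be excluded from the accuracy analysis, and it is cheap.

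**What to change.** In Form 3 (Appendix N), Table 3:

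1. For Boxes 346–348 and 351–353, replace the total of 99 with *three times the number of included subjects (255 at 85)*. Do not fix it at 255, because up to 93 subjects are permitted.
2. Replace 22–44 with Appendix O's 57–113 for 85 subjects, scaled in proportion if more are included (62–124 at 93).
3. State that Appendix O governs the distribution check.
4. Keep the overall-range requirement (systolic ≤100 to ≥170, diastolic ≤50 to ≥120) as a separate reason for Distribution replacement.

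In the same edit:

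5. Reconcile the other 33-subject values: Form 2's threshold of 12 for Boxes 221 and 222; Form 3's 33 in Boxes 312 and 330, and the 10–12 per range and totals of 33 in Boxes 314–323; the minimum of 10 per sex at Box 330; and Table 5's pass requirements and its references to 33 subjects and 99 differences. Changing Table 3 alone would leave one form with 255 readings in one table and 33 subjects in another.
6. Review the maximum difference of 19 in Data Checking, Form 3 and Appendix O. Either rescale it (about 49 at 255 readings) or say that the stricter limit is intended and that 57–113 is then redundant.

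The cost is an edit to the forms and a sentence on precedence. Items 1–4 need no added subjects or measurements.

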Appendix O – International Protocol Accuracy Criteria

ESH International Protocol 2010			
Sequential Measurements			
IP Grading Part 1 - Minimum Requirements (at least 255 pairs of individual measurements)			
N	≤ 5 mmHg	≤ 10 mmHg	≤ 15 mmHg
Two of	188	224	247
All of	167	209	240
IP Grading Part 2 (85 subject mean pressures)			
N	$2/3 \leq 5$ mmHg		$0/3 \leq 5$ mmHg
At least	62		
At most			8
Recruitment Ranges (n = 85)			
SBP		DBP	
mmHg	Subjects	mmHg	Subjects
90*...129	26 – 31	40*...79	26 – 31
130...160	26 – 31	80...100	26 – 31
161...180*	26 – 31	101...130*	26 – 31
*	Altogether, up to 4 recruitment pressures are permitted to be outside these limits.		
Test Measurement Distribution			
SBP		DBP	
mmHg	Measurements	mmHg	Measurements
≤ 100	≥ 3	≤ 50	≥ 3
< 130	57 – 113*	< 80	57 – 113*
130...160	57 – 113*	80...100	57 – 113*
> 160	57 – 113*	> 100	57 – 113*
≥ 170	≥ 3	≥ 120	≥ 3
*	The difference between the maximum and minimum of these 3 counts for SBP and, separately, for DBP, must be less than or equal to 19.

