3. Blood pressure range: 26 to 31 subjects in each of the three SBP and three DBP recruitment ranges as shown in Form 3 – Study Results (**Appendix N**):
 - Low blood pressure (systolic: 0-129, diastolic: 0-79)
 - Medium blood pressure (systolic: 130-160, diastolic: 80-100)
 - High blood pressure (systolic: 161 or higher, diastolic: 101 or higher).

Participant Remuneration

To thank participants for their valuable time, they will be provided with a \$50 VISA pre-paid gift card at the end of the study visit.

Recruitment Methods

Recruitment flyers (**Appendix E**) will also be posted in public spaces at corporate offices and medical clinics, who have agreed to participate within Central Ontario, including Markham, Toronto, and North Simcoe Muskoka.

Recruitment emails (**Appendix F**) will be sent to all relevant employees located at corporate offices and medical clinics, who have agreed to participate within Central Ontario, including Markham, Toronto, and North Simcoe Muskoka, with a link to [contact] to indicate interest. Recruitment will be a two-step process.

Clinical staff, from clinics who have agreed to participate, will be provided with a short script (**Appendix G**) and Frequently Asked Questions (FAQ) document (**Appendix H**) to assist with the recruitment process. Individuals interested in participating can submit a consent to contact form (**Appendix I**) to the clinic staff, who will scan and send the forms to the research team. **Research assistant** will call individuals who had expressed their interest in participating to further explain the study (**Appendix J**) and ask if they would like to participate. The research assistant will then inform them about the consent form (**Appendix K**) that they will be asked to sign at the study site. The research assistant will provide the participant with information about a scheduled time for participating in the study and directions.

Interactions with participants and Data collection

Form 1 - Device information

Prior to the first interaction with a participant, the supervisor will fill in the information about the device in Form 1 of the ESH-IP (**Appendix D**). As noted above, the Contec CMS50EW device is an electronic finger pulse oximeter (Contec Medical Systems Co., Ltd, Qianhuangdao, China) that generates a PPG, which is then sent to HeartBeat's proprietary algorithm to calculate blood pressure.

Confirmation of appropriate setting conditions

[figure not shown]

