2. Ensure the overall systolic blood pressure is within the range of ≤ 100 to ≥ 170 mmHg and the overall diastolic blood pressure is within the range of ≤ 50 to ≥ 120 mmHg.
3. If the participants have a blood pressure outside the range of 90–180mmHg for systolic blood pressure and 40–130mmHg for diastolic blood pressure, only a maximum of 4 blood pressures readings outside of this range can be included in the analysis.
4. Ensure there are approximately 26-31 participants in each of the 3 blood pressure ranges (low blood pressure (systolic: 0-129, diastolic: 0-79), medium blood pressure (systolic: 130-160, diastolic: 80-100) and high blood pressure (systolic: 161 or higher, diastolic: 101 or higher)).

Data Analysis

[figure not shown]
The profile of the study participants will be described based on a demographic analysis conducted on data collected from the subject data form from the ESH-IP (**Appendix M**).

All collected data on Forms 1 and 2 will be sent to the researchers at the SE Research Centre, who will consolidate the data from the Forms 1 and 2 and analyze the data as specified in Form 3, the Study Results form from the ESH-IP (**Appendix N**) (O'Brien et al., 2010).

In order to pass the validation process, the device must pass both parts 1 and 2 based on the accuracy criteria table (**Appendix O**).

Plots

These are mean-difference plots, and the plots modelled from the data collected should be exactly as shown in the example plots below.

The x-axis of these plots represents blood pressures in the systolic range 80mmHg–190mmHg and the diastolic range 30 mmHg–140 mmHg. The y-axes represent errors from – 30mmHg to +30mmHg. Horizontal reference lines will be drawn at 5mmHg intervals from +15mmHg to – 15 mmHg. The mean of each device pressure and its corresponding observer pressure will be plotted against their difference with a point. Differences greater than 30mmHg will be plotted at 30 mmHg. Differences less than – 30mmHg will be plotted at – 30 mmHg. The same scales will be used for both SBP and DBP plots. Where points are superimposed, these will be indicated either by proportionately larger points or by different symbols.

5. Confidentiality and security of data

Electronic data

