- ☞ If possible, a permanent record of device measurements should be kept. If software is provided, device measurements should be downloaded daily.

Recruitment details

Date and time	201	Study number and Subject number	202	203
Date of birth	204	Age	205	
Sex	Male 206	On antihypertensive medication	Yes 207	No 207
Arm circumference cm	208	Cuff for test device	Standard 209	Other 209
Wrist circumference cm	210	Height ft, in		Weight lbs

Box 209: This is only required for arm devices. If the arm circumference is such that no suitable cuff is available, circle *Cuff size unavailable* in Box 287 and exclude the subject.

Box 210: This is only required for wrist devices.

Entry measurements

Ask the subject to relax for 10–15 min. Then make sure that the subject is seated with legs uncrossed and back supported. Ensure that the arm is supported at heart level. If a wrist device is being tested, the wrist must be supported according to the manufacturer's instructions. If the subject is not seated as described, the posture used must be recorded as a protocol adjustment.

BPA	Observer 1		Observer 2		Device		Heart Rate bpm	
	SBP	DBP	SBP	DBP	SBP	DBP		
	211	212		213	214		215	216
	Observer Mean			Category			Count	
BPA	SBP	DBP	SBP	DBP	SBP	DBP		
	217	218	LL L M H HH 219	LL L M H HH 220	221	222		

Boxes 217, 218: Enter the rounded up averages of Boxes 211 and 213 and of Boxes 212 and 214 respectively.

Box 219: Circle the range according to the BP in Box 217. LL: < 90, L: 90–129, M: 130–160, H: 161–180, HH: >180.

Box 220: Circle the range according to the BP in Box 218. LL: < 40, L: 40–79, M: 80–100, H: 101–130, HH: >130.

Boxes 221, 222: Update the running totals, for the ranges (counting LL and L together and counting HH and H together) in Boxes 219 and 220, and enter them respectively.

- ☞ If both Box 221 and Box 222 are greater than 12 or if an *LL* or *HH* is circled and there are already 4 such items circled, circle *Ranges complete* in Box 287 and exclude the subject.

- ☞ If one of Box 221 or Box 222 is greater than 12 but the other is not, it may be necessary to include this subject, and remove another, in order to achieve the correct range distribution; in the removed subject, circle *Range adjustment* in Box 287.

Validation measurements

	BP1		BP3		BP5		BP7	
	SBP	DBP	SBP	DBP	SBP	DBP	SBP	DBP
Observer 1	223	224	225	226	227	228	229	230
Observer 2	231	232	233	234	235	236	237	238
Observer mean	239	240	241	242	243	244	245	246

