Box 308: The number of subjects excluded with *Cuff size availability* circled in *Box 287*.

Box 309: The number of subjects excluded with *Observer disagreement* circled in *Box 287*.

Box 310: The number of subjects excluded with *Distribution* circled in *Box 287*.

Box 311: The number of subjects excluded with *Other reasons* circled in *Box 287*. A summary of those reasons must be provided in Box 313.

Box 312: The total recruited equals the number screened (Box 301) less the number excluded (Box 302). This should equal 33 except in validations in some specific populations.

Box 313: A summary of why those counted in Box 311 were excluded (*Box 288*).

Boxes 314–323: In a completed study in a general adult population, the sum of Boxes 314 and 315, Box 316, the sum of Boxes 317 and 318, the sum of Boxes 319 and 320, Box 321 and the sum of Boxes 322 and 323 must each be between 10 and 12. The sum of Boxes 314, 318, 319 and 323 must be at most 4. The sum of Boxes 314–318 and the sum of Boxes 319–323 must each be exactly 33. Studies in specific populations may have different restrictions and totals (*Boxes 219 and 220 – Form 2 for each included subject*).

Boxes 324–329: The number of subjects in each range on antihypertensive medication (*Boxes 207, 219 and 220*).

Table 2 Subject details

Sex	Male : Female	330	
Age (years)	Range (Low : High)	331	
	Mean (SD)	332	
Arm circumference (cm)	Range (Low : High)	333	
	Mean (SD)	334	
Cuff for test device (Upper arm devices only)	Small	335	— — cm
	Standard	336	— — cm
	Large	337	— — cm
	Other	338	— — cm
Wrist circumference (cm) (Wrist devices only)	Range (Low : High)	339	
	Mean (SD)	340	
Recruitment BP (mmHg)	Range (Low : High)	341	SBP
		342	DBP
	Mean (SD)	343	
		344	

Note: The values in Boxes 314–380 refer only to the final recruited subjects, each of whom contributes SBP and DBP measurements for analysis. Excluded subjects are not included in any of this analysis.

Box 330: Enter the number of males, a colon and the number of females. They should total 33 except in validations in some specific populations. If the minimum requirements (10 for a general population) are not met, subjects must be replaced as necessary (Box 206).

Box 331: Enter the age of the youngest subject, a colon and the age of the oldest subject e.g. 31:74. Subjects outside the required range (25 and over for a general population) are not permitted (Box 205).

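### Appendix O's pass marks are fixed counts that fit only 85 subjects and 255 pairs, yet the plan sets both sizes as minimums and its quotas, read literally, can end at 86 to 88

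*Combined protocol and SAP*

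**What the plan says.** - **Decision rule.** Data Analysis states that "the device must pass both parts 1 and 2 based on the accuracy criteria table", which is Appendix O.
- **Size of the data set.** Appendix O heads Part 1 "IP Grading Part 1 - Minimum Requirements (at least 255 pairs of individual measurements". The first recruitment quota is "Numbers: At least 85 who fully complete the study protocol, and fall within the parameters listed in #3". Both are minimums.
- **When recruitment stops.** "Recruitment will continue until the following quotas are met"; the third quota asks for "26 to 31 subjects in each of the three SBP and three DBP recruitment ranges". The daily check under Data Checking repeats the 26–31 figure but qualifies it as approximate.
- **Signs that 85 is meant.** Appendix O labels its recruitment table n = 85 and refers to 85 subjects in the Part 2 heading.
- **Forms 2 and 3.** These still carry the 33-subject design. Form 2 excludes a subject "If both Box 221 and Box 222 are greater than 12". If only one count is over 12, it allows the new subject to be taken and another removed (Range adjustment). Form 3 says the range totals "must each be exactly 33".
- **Scaling.** A note to Form 3, Table 3 reads "In validations carried out in specific populations requiring more than 33 subjects but with similar blood pressure distributions, similar proportions should be used". A similar note under Table 5 covers the pass marks and is also limited to specific populations.

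**The concern.** A pass mark printed as a count is a required proportion only at one denominator. If 86 to 88 subjects complete and are all analysed, the same counts ask for a smaller share of accurate readings. If 85 of them are analysed, the marks hold, but someone must decide which subjects to leave out. The visible text accommodates both courses and says how to carry out neither. The choice would then be open after device readings have been seen. It bears directly on the verdict, and Section 2 says that a favourable result leads to applications to Health Canada and the FDA.

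**Working it through.** **1. Reproduce the printed marks.** Inputs: Form 3, Table 5 (33 subjects, 99 pairs) and the Appendix O sizes. Part 1 mark = Form 3 count × 255/99; Part 2 mark = Form 3 count × 85/33.

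| Mark | Form 3 | Scaled | Appendix O |
|---|---|---|---|
| Two of, ≤5 / ≤10 / ≤15 mmHg | 73 / 87 / 96 | 188.03 / 224.09 / 247.27 | 188 / 224 / 247 |
| All of, ≤5 / ≤10 / ≤15 mmHg | 65 / 81 / 93 | 167.42 / 208.64 / 239.55 | 167 / 209 / 240 |
| 2/3 within 5 mmHg, at least | 24 | 61.82 | 62 |
| 0/3 within 5 mmHg, at most | 3 | 7.73 | 8 |

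Nearest-integer rounding gives all eight. The measurement bounds follow in the same way: 22 and 44 × 255/99 = 56.67 and 113.33, printed as 57–113.

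**2. Where can recruitment stop?** Take the quotas literally: at most 31 per range, stop once N ≥ 85 and every range holds at least 26.

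- 31 + 31 + 23 = 85 fails the minimum of 26, so recruitment continues to 31 + 31 + 26 = 88.
- Enumerating all paths gives 85 (for example 28/28/29), 86 (26/29/31 or 26/30/30), 87 (26/30/31) and 88 (26/31/31).
- The number and range quotas cannot push past 88. With two ranges capped at 31, the third holds at least 88 − 62 = 26. Only an unmet sex quota, or recruiting past the stop point, could go further.

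**3. What the unchanged counts require.** Share = count/(3N) for Part 1 and count/N for Part 2.

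| N | Two of (%) | All of (%) | 2/3 minimum (%) | 0/3 maximum (%) |
|---|---|---|---|---|
| 85 | 73.7 / 87.8 / 96.9 | 65.5 / 82.0 / 94.1 | 72.9 | 9.4 |
| 86 | 72.9 / 86.8 / 95.7 | 64.7 / 81.0 / 93.0 | 72.1 | 9.3 |
| 87 | 72.0 / 85.8 / 94.6 | 64.0 / 80.1 / 92.0 | 71.3 | 9.2 |
| 88 | 71.2 / 84.8 / 93.6 | 63.3 / 79.2 / 90.9 | 70.5 | 9.1 |

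Seven marks loosen. The 0/3 limit tightens slightly.

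**4. Effect on the verdict.** The documents give no error SDs, so these are assumptions. The simulation used normal errors, no mean bias, readings rounded to whole mmHg, each device reading compared with the nearer of the adjacent observer values, and Parts 1 and 2 for one pressure component. SDs are between-subject / within-subject device / observer, in mmHg. The last column compares verdicts on the same data from all 88 and from the first 85 enrolled, both with the fixed counts.

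| SDs | Pass at 88, fixed counts | Pass at 88, proportional marks | All 88 v first 85: verdicts differ |
|---|---|---|---|
| 4/6/3 | 0.61 | 0.32 | 28% |
| 5/5/3 | 0.58 | 0.38 | 21% |
| 5/4/3 | 0.75 | 0.69 | 9% |
| 5/3/3 | 0.74 | 0.73 | 1–5% |
| 6/3/3 | 0.19 | 0.17 | 1–5% |
| 3/5/3 | 1.00 | 0.99 | 1–5% |

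The levels are sensitive to the model. Without rounding, the first two rows become 0.23 v 0.07 and 0.26 v 0.11.

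**The case against.** **The plan means 85 and has a way to hold it.** The 33-subject design faces the same difficulty (12 + 12 + 9 = 33 fails its minimum of 10), and Form 2 answers it with Range adjustment. The protocol says it follows that source method closely, and Appendix O's labels point to 85. This largely stands as a statement of intent. It does not settle the matter. The step is still triggered at 12, it is worded as something that may be necessary, and nothing says which subject is removed. The Distribution rule in Form 3 replaces subjects for drift or overall range; it does not trim a compliant set of 86 to 88.

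**A reader might infer that overshoot is the usual outcome.** A simulation that turns candidates away at 31 per range and never removes anyone ends above 85 in 76–78% of runs with an even candidate mix, and in over 99% with a 50/35/15 mix. The documents do not support that inference. They give no candidate mix, they contain an include-and-remove step, and they soften the quota to an approximate one. When each candidate accepted after the 85th displaces a removable subject, every simulated run ended at 85.

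**Proportionality is already the principle.** Appendix O is itself a proportional scaling, so an analyst with 88 subjects has a precedent. That supports the fix. But both scaling notes are confined to specific populations, neither is tied to Appendix O, and Data Analysis points to the printed counts.

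**Part of the disagreement is noise.** The first 85 and last 85 of the same 88 disagree in 0.4–8% of runs, so differences of 1–5% carry no weight. The 21% and 28% figures lie well beyond that.

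**Conclusion.** The point holds as a gap in a stated decision threshold. The marks are correct at 85 subjects and too lenient in seven of eight places at 86 to 88. The plan allows those numbers on a literal reading and neither fixes the analysed number nor rescales the marks. The arithmetic rests only on the documents.

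Two limits apply. The frequency of ending above 85 is unknown. The effect on passing rests on assumed SDs: it is material in two of the six settings tried and 0.07 or less in the other four. A reader might conclude that the rule generally favours the device. The evidence supports only that it can do so for some borderline devices when the number exceeds 85. It should be fixed, since the cost is small and the marks decide the study.

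**What to change.** **Preferred.** In Appendix O and Data Analysis, state the marks as fractions of the pairs and subjects actually analysed, rounded to the nearest integer:

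- two of 73/99, 87/99, 96/99;
- all of 65/99, 81/99, 93/99;
- at least 24/33 and at most 3/33;
- measurement bounds 22/99 and 44/99.

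Say that the limit of 19 on the difference between range counts stays as printed. Nothing changes at 85. At 88 (264 pairs) the marks become 195/232/256, 173/216/248, 64 and 8, with bounds 59–117.

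**Alternative.** State that exactly 85 subjects are analysed, change the Part 1 heading from a minimum to 255 pairs, and update the Range adjustment trigger from 12 to 31. Any removal must be chosen without sight of device readings or device–observer differences. The retained 85 must still meet the range and sex quotas, the minimum of 3 readings at each extreme, the 57–113 bounds and the limit of 19. A rule that looks only at range and sex is not enough, because trimming could break one of the other conditions.

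**In either case,** replace the leftover 33-subject figures in Forms 2 and 3 with the matching ones: the cap of 12, 10–12 per range, the total of 33, 99 pairs, 22–44 and the Table 5 marks.

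**Cost.** A short paragraph and about 20 figure edits. No extra subjects are needed, and no pass mark changes at 85.
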